7. OUTLINE OF STUDY VISITS

Baseline Visit (SA 1 and 2, Table 1). After informed consent, eligible participants will be scheduled to arrive for an overnight visit in the DCRU/CRU within a standardized time interval (< 2 weeks) from informed consent. During the evening, participants will undergo questionnaire administration, blood pressure measurements, application of the MultiSense™ monitoring device, and anthropometry. They will be provided dinner and undergo polysomnography (PSG). In the morning, participants will undergo fasting venipuncture, overnight urine collection, ECHO, 6 minute walk test and blood pressure measurements. For those with PAF (cases), hook-up for continuous ECG monitoring will be performed along with education regarding how to handle the device and bathing instructions, etc. All measurements in the DCRU/CRU will be performed blinded to PAF status. The only unblinded staff will be a dedicated research assistant who will perform the ECG monitoring hook-up. Blinded staff will collect and process data and perform data entry. After the baseline visit, participants with PAF (n=150) will undergo hook-up of the ECG monitor and an activity monitor at the baseline visit to wear for a 7-21 day period. The monitors will be picked up by a courier service. If eligible for the 7T MRI sub-study (cases - AHI \geq 15 and agree to CPAP treatment, controls AHI \geq 15), they will be consented and all questions answered. The individuals who serve as controls who are identified to have sleep apnea (AHI \geq 5) or for those with PAF who have an AHI ranging from 5-15 on the baseline sleep study in the Clinical Research Unit will be notified of these results and the physician will be contacted if the participant provides permission.

Table 1. Timeline of Events for SA 1 and 2	
EVENING	
5PM	DCRU/CRU Arrival/Intake
515PM	Questionnaire Administration
600PM	Anthropometry
630PM	Dinner
9PM	PSG Hook-Up
10PM	Blood Pressure Measurements in Triplicate
1030PM	Lights Out-Overnight PSG
7AM	Lights On/Blood Pressure Measurements in Triplicate
715AM	Fasting Venipuncture
745AM	Overnight Urine Collection
8AM	Echocardiography
830AM	Breakfast
9AM	Continuous ECG monitoring hook-up and education for cases with PAF
930AM	DCRU/CRU Discharge

[figure not shown]
Follow-Up Visit (SA3). Those with SDB (AHI $>$ 15) without evidence of central apnea (central apnea index $>$ 5) or Cheyne Stokes Respirations via baseline visit PSG and who have PAF will undergo the following:

1. A 5-7 day home-based auto-titration (APAP, Resironics Autopap System One with humidifier) to identify the optimal positive airway pressure (PAP) setting will be performed (with settings 4-20cm H₂O).
2. Participants will be educated on the use of PAP and mask fit will be optimized.
3. The research assistant will maintain contact with the participant by telephone during the 5-7 days. The research assistant will contact the participant within 24 hours and then again within the 5-7 period. During the first 24 hours the overnight data will be

reviewed and ascertained for the presence of treatment emergent central apnea. If a central apnea index >5 is noted during the first night initial exposure to CPAP, then the participant will be withdrawn from the study. The participant will be notified about the results of the research study testing and will be encouraged to follow-up with his/her physician. The participant's physician will be contacted provided that the participant provides permission.

4. At the end of the 5-7 day titration, the data on pressure responses and PAP use (with no patient identifying information) are transmitted using a wireless feature from the patient's home to a secure web-site which is accessible by the research staff. If wireless coverage is unavailable, data may be transmitted using a standard phone line or directly retrieving a data card from the machine. The PI will review the data and identify the optimal pressure. If the initial APAP study is unacceptable, a repeat 5-7 day recording will be performed. The goal will be to identify the pressure that results in an $AHI < 5$ events/hour (optimally), however, < 10 events/hour would be deemed acceptable. For those participants that have mask leak or interface issues, they will undergo troubleshooting by the coordinator by phone and in-person as needed. If despite addressing these issues, the AHI remains ≥ 10 , then the participant will be withdrawn from the study and will be encouraged to follow-up with his/her physician. The participant's physician will be contacted provided that the participant provides permission. If the participant qualifies for CPAP, then the subject will be approached to assess interest in the MRI sub-study.
5. The research assistant will re-set the device to deliver this optimal fixed pressure identified by the PI through the secure wireless web-site. The web-site will allow the research assistant to measure adherence daily and review with the participant at the scheduled follow up calls to maximize PAP use. Each APAP also contains a "smartcard" which will provide objective adherence data if wireless is not available. The participant contact during follow-up will be as follows: the participant will be called every 2 weeks thereafter during the 3 months period of CPAP usage or more frequently as needed to address CPAP adherence issues. An in-person visit will be scheduled for those participants that have non-adherence due to mask fit/leak noted on more than 2 consecutive nights.
6. An overnight DCRUCRU visit will be scheduled after 3 months of wearing CPAP (*this duration chosen based upon data supporting immediate influences of apnea on PAF⁷¹ and CPAP effects on cardiac function in 1 month⁷⁸) during which the same measures performed at the baseline visit will be collected. If the participant had a 7T MRI at their baseline visit, a follow-up MRI will be scheduled.

As SDB prevalence of ~50% has been noted in those with AF⁶⁴, we estimate that ~75 participants will meet criteria to proceed to CPAP. If this goal is not met, then we will supplement recruitment from the sleep disorders program (~1200 studies/year) to identify those with SDB who have PAF to achieve this goal.

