8. STUDY PROCEDURES AND DATA COLLECTION

2-DIMENSIONAL DOPPLER ECHOCARDIOGRAPHY. **Procedure:** Participants will be studied by one of two senior sonographers during quiet respiration in the left lateral decubitus position with administration of intravenous agitated saline to enhance imaging. Parasternal, apical and subcostal 2-D views and apical 3D views will be obtained with transducer orientation and gain settings adjusted to optimally define endocardial surface of each cardiac chamber. Measurements will be performed by the Director of the ECHO Lab (accredited by the Intersocietal Commission for the Accreditation of Echocardiography Laboratories), [name] (Co-I) and designate off-line (HeartLabs Inc, Q Labs, Phillips Medical) in a blinded fashion on 3 representative beats and the results averaged. Measurements will be performed according to the American Society of Echocardiography recommendations ^{79,80}. Studies will be archived on CD. Rigorous quality control measures will be used including random repeat measurements to calculate inter- and intra-observer reliability.

Approximately 20% of echocardiograms result in suboptimal views in at least 2 of 6 myocardial segments of the left ventricle in apical views. The use of a contrast agent can opacify the sub optimally viewed areas allowing for better analysis. Individuals with obesity, lung disease, or other critical care areas usually require the use of a contrast agent for optimal echocardiogram views. Subjects requiring a contrast dye will be administered an IV dose of Definity ® (perflutren lipid microsphere injectable suspension), a US Food and Drug Administration (FDA) approved contrast dye. Subjects will be screened for known contraindications: known or suspected cardiac shunts or patent foramen ovale, or known hypersensitivity to perflutren. Subjects will also be informed of the potential risks

associated with Definity ® as described in the informed consent document.

Relevant ECHO Variables:

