
3) 7-21 Day CONTINUOUS ECG MONITORING.

Procedure: A 3-lead (2 channel), wireless, lightweight (3.2 ounce) ECG monitoring device (Heartrak External Cardiac Ambulatory Telemetry ®) will be used to collect the ECG data over a 7-21 day period in those with PAF after the baseline and follow-up DCRU/CRU visits. The device is: 3x7", bandwidth: 0.05-30 Hz, sampling rate=205 Hz, stores 30 days of

data, 30 feet transmission mode and memory hold of 10 years with a <1% data transmission failure and data loss in field testing. 7-21 day was chosen given the variability of PAF and because ECG monitoring >48 hours is reasonable to capture AF paroxysms ⁹⁴. **ECG Sensor Application**. This will be performed by a trained technician. Participants will be asked to remove clothing from the waist up to attach the sensors to the chest. Staff will ensure privacy by covering the participant with a sheet or gown. The staff will shave necessary areas on the chest prior to sensor application to ensure that the sensors stick closely to the skin and will provide the participant with the ECG monitor/holster/clip, leads, communicator and charger, electrodes and a handbook with simple pictorial/written educational instructions.

At-home ECG Monitoring Logistics. The ECG monitor box may be clipped to a belt or pocket, and the communicator may be placed in a pocket (much like a cell phone). The participant will be instructed to engage in usual activities and instructed to remove the monitor before bathing and reapply the sensors after bathing. An ECG technician will be available by phone 24-7 to address issues with device malfunction, lead placement and replacement of equipment. Research staff will contact the participants every 3-4 days to assess for symptoms and help troubleshoot any mechanical or logistical issues. ECG quality grade data will be collected: (excellent: >90% of ECG data without artifact, good: 70-90% without artifact, fair: 50-70% without artifact, poor <50% artifact free).

Relevant ECG Variables: AF paroxysm frequency will be scored by a certified ECG technician and categorized by sleep vs. wake states based upon self-report from the ECG log. This will allow for assessment of AF burden temporal patterns via 7-21 day ECG monitoring relative to SDB. These ECG data will also be analyzed by [name] group, including [name] and [name], if there is insufficient NSR data from the PSG ECG to perform HRV analyses.

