c) The *Sleep Habits and Medical Condition Questionnaire*¹⁰¹, which includes comorbidities, medication use (including anti-arrhythmic medications), caffeine use, smoking, alcohol use, etc., d) The *Medical Outcomes Survey-SF 36 (MOS-SF)*¹⁰², a standardized tool for assessing general health status, physical and social functioning, and fatigue, e) *Patient Health Questionnaire-9 (PHQ-9)*, which assesses depression symptoms. It has ten questions where the answers will be added to indicate severity of depression. The Research Assistant will score depression questionnaires and if the score is indicative of depression (10 or greater) the Research Assistant will then contact a study physician who will determine appropriate referrals and responses and contact the participant to advise him to seek medical/psychiatric consultation. If there was any indication that a participant was in imminent danger to himself or others, the participant would be advised to go to the nearest emergency room for evaluation by a psychiatrist. If signs of depression, anxiety or other psychological disorders were evident without evidence for immediate risk, the participant would be advised to contact a psychologist for further evaluation. f) *Daily ECG/Activity Log*, which will be completed during 7-21 day ECG monitoring including data on sleep/wake times including naps, periods of vigorous activity, caffeine use, alcohol use, smoking, monitor removal time and symptoms (e.g. palpitations, dyspnea, chest pain) g) *Atrial Fibrillation Effect on Quality-of-life*, a 20-item questionnaire that assesses the impact of atrial fibrillation on quality of life.

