SA2. Examine patterns of PAF burden via 7-21 day continuous ECG monitoring relative to SDB. We will model the relationship between mean frequency AF paroxysm variation and SDB (e.g. AHI considered as a continuous variable). A linear regression model will be used to assess possible quadratic and threshold effects of SDB on variation. These models may also include sleep state by SDB interaction terms (along with the state indicator) to examine if the effect of SDB on variation differs by sleep state. Maximum likelihood (based on a normal distribution for variation if appropriate) will be used to fit models, and the Akaike Information Criterion (AIC) will be used to select the best fitting model. Estimates of the effect of SDB on variation (and corresponding 95% CI) will be obtained based on the selected model.

SA3. Examine the effects of SDB (AHI \geq 15) treatment for 3 months on AF paroxysm frequency and also measures of autonomic function, cardiac morphology, biochemical measures in those with SDB and PAF. For this subgroup of SDB (AHI \geq 15) and PAF, we will perform paired t-tests to compare pre- and post-treatment mean outcomes (Primary outcome: AF paroxysm frequency from 1-week ECG monitoring) and also ECHO and biochemical measures. For any outcome for which a departure in normality is found (based on the Shapiro-Wilk test) but a transformation of the outcome cannot be found to adequately address the issue, we will use the Wilcoxon signed rank sum test to detect a difference in the distribution of the pre- and post- responses. This assessment is not intended to be confirmatory, but rather to provide estimates of variability and effect sizes to inform future studies/randomized trials. Linear regression models will then be developed to model PAF burden at the 3 month visit by conditioning on baseline PAF burden, baseline SDB,

and time from baseline to 3 month visit. Additional adjusted models will carefully consider the covariates list above.

POWER BY AIM.

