A Safety Monitor will be assigned to the study (UHCMC, [name] MD and at CCF, [name] MD), who will review adverse events and data targeted by the research coordinator to assist with adverse event adjudication and also to ensure that no physiological (e.g., blood pressure) findings warrant immediate intervention. If so, the participant/family will be contacted and advised of the findings and offered assistance with appropriate referrals. Adverse events (classified by severity and unexpected/expected) will be defined and reported to the IRB, NIH, and the Safety Monitor in accordance with the rules regulating each severity class (expected vs. unexpected, serious vs. other; related vs. unrelated).

On a weekly basis, the P.I. will review all data collected, including logs of phone calls between the coordinator and participant, ECG data and biochemical levels from blood tests.

Elucidation of the Influence of Sleep Apnea on Risk of Atrial Fibrillation PI- [name] and [name]

If any serious adverse events occur, these will be reported to the IRB and NIH. All data from clinical assessment, physiological measurements, and biochemical measurements will be transferred to a computerized database in a dedicated instance of Physio-MIMI. Data completeness and accuracy are monitored by: 1) technician review of data at the time of the study; 2) review of raw and processed data by the coordinator prior to data entry; 3) data entry with form-configured screens and on-screen logic/range checks; 4) double data entry; 5) review of outliers and additional logic checks with statistical software. Discrepant entries will be verified by reviewing the raw data. Manuals will detail the protocol and all procedures, including recruitment, data collection, data transfer, specimen collection, and data management.

The P.I. will assure that research staff (research coordinator, research assistant, polysomnologist, sleep technologist and CRU nurses) undergo rigorous training, undergo re-training and re-certification periodically (at least every 6 months or more frequently if excessive variation is seen). Sleep studies are scored and processed by certified polysomnologists blinded to the identity of the participant using standardized procedures.

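### SA3 has no stated masking to visit or CPAP: the defined blind is to PAF status, which is constant in SA3, and no blind is stated for AF paroxysm scoring, its primary outcome

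*Combined protocol and SAP*

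**What the plan says.** Three places describe blinding of the measurements.

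- **Section 7, Baseline Visit.** "All measurements in the DCRU/CRU will be performed blinded to PAF status". The next sentence adds: "The only unblinded staff will be a dedicated research assistant who will perform the ECG monitoring hook-up". The Follow-Up Visit (SA3) text repeats the baseline measures after three months of CPAP and mentions no masking to visit or treatment.
- **Section 8, echocardiography.** Measurements are made off-line by the echo laboratory director or a designate, "in a blinded fashion on 3 representative beats and the results averaged". The text does not say what the reader is blinded to. Studies are archived.
- **Section 13.** "Sleep studies are scored and processed by certified polysomnologists blinded to the identity of the participant using standardized procedures".

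For the continuous ECG, Section 8 item 3 says only that "AF paroxysm frequency will be scored by a certified ECG technician"; no blind is stated.

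Sections 9 and 10 define SA3 as a paired pre/post comparison of AF paroxysm frequency (primary), autonomic function, cardiac morphology and "biochemical measures in those with SDB and PAF". Left atrial volume is the primary echo measure in Table 2. SA3 is described as non-confirmatory, with the purpose of giving variability and effect-size estimates for later trials.

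**The concern.** A blind is useful only if it hides the factor being compared. In SA1 that factor is PAF status. In SA3 it is visit, which is the same thing as CPAP exposure, because only PAF patients who start CPAP have a scheduled second visit. The blind defined in Section 7 therefore does no work in SA3, and nothing else in the documents clearly does it instead.

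SA3 has no concurrent untreated group. In a controlled trial, a reader's drift over time would fall on both arms and largely cancel. Here a consistent tendency to count fewer paroxysms, or trace a smaller atrium, on the second study cannot be told apart from a CPAP effect. Since SA3's output is effect sizes for later trials, the harm is a biased planning figure more than a false claim of efficacy.

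**Working it through.** **1. Which factor each blind hides**

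| Measurement | Stated blind | Hides visit/CPAP? |
|---|---|---|
| Research-unit measurements (Section 7) | PAF status, under Baseline Visit | No; PAF status is constant in SA3 |
| Echo reading (Section 8) | Blinded, object not given | Not stated |
| AF paroxysm scoring (Section 8) | None stated | Not stated |
| PSG scoring (Section 13) | Participant identity | Not stated; matters mainly for SA1 |

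**2. The plan's SA3 power figure**

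Inputs (Sections 9 and 10, Power by Aim): n = 75, coefficient of variation 1.5, pre/post correlation 0.8, target ratio 0.83, paired t-test, two-sided 0.05, stated power 83.1%.

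Taking the correlation on the raw scale of a log-normal outcome, the SD of the log difference is

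sqrt(2 × [ln(1 + 1.5²) − ln(1 + 0.8 × 1.5²)]) = sqrt(2 × [ln 3.25 − ln 2.80]) = 0.546.

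The standard error is 0.546/√75 = 0.0630. The noncentrality is |ln 0.83|/0.0630 = 0.1863/0.0630 = 2.96 on 74 df, giving power of 83.07%. The stated figure is reproduced. An observed ratio of about 0.88 or lower is significant.

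**3. Illustration: no CPAP effect, but second-visit counts read low**

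The shift sizes are assumptions. A shift of b gives noncentrality −ln(1 − b)/0.0630.

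| Post-CPAP counts read low by | Shift in SDs of the log difference | Chance of p<0.05 (nominal 5%) |
|---|---|---|
| 2% | 0.037 | 6% |
| 5% | 0.094 | 13% |
| 8% | 0.153 | 26% |
| 10% | 0.193 | 38% |

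If the correlation of 0.8 is placed on the log scale, the SD is 0.687. The plan's power then comes out at 64.0% and is not reproduced, and the 5% and 10% rows become about 10% and 26%.

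**4. Illustration: effect on a later trial's planning figure**

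Suppose the true ratio is 0.83 and post-CPAP counts are read 5% low. The expected estimate is 0.83 × 0.95 = 0.789. With the SD fixed, sample size goes with the inverse square of the log ratio, so a trial sized on 0.789 would enrol (ln 0.83/ln 0.7885)² = (0.1863/0.2376)² = 61% of the patients needed. At 10% low the estimate is 0.83 × 0.90 = 0.747, and the fraction is (0.1863/0.2917)² = 41%.

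**5. SA1 residual**

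The PSG montage in Section 8 item 2 includes an ECG channel, and the electronic-records text in Section 6 foresees AF appearing on overnight monitoring. Blinding to identity does not hide AF on a trace being scored. The item's definitions use effort for apnea type, amplitude reduction with desaturation or arousal for hypopneas, and waxing and waning airflow or inductance for periodic breathing. None uses the ECG.

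**The case against.** Four points on the other side have weight.

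- **There is more than one blind.** A reader might infer that PAF status is the only thing masked anywhere, or that echo readers are known to be unmasked to visit. The documents support neither. Echo reading is blinded with its object unstated, and PSG scoring is blinded to identity. Section 11 also says the cores receive nothing that identifies participants. This stands: the echo gap is unspecified masking, not shown absence. It does not supply a visit mask, and it does not touch AF scoring, for which no blind is stated.
- **Procedure manuals may hold the detail.** Sections 8 and 13 refer to manuals that are not part of these documents. Masking rules may be there, but the protocol should state what protects its SA3 primary outcome.
- **The shifts are assumed.** A uniform 10% misreading is 0.1054/0.1863 = 57% of the whole target effect on the log scale. The smaller rows are the more cautious reading, and nothing here is calibrated to left atrial volume.
- **SA3 is non-confirmatory, and some outcomes leave little to judgement.** HRV is largely automated, and blood assays are run in batch and in duplicate. This limits the concern to AF counts and echo. It does not excuse bias in effect sizes, which are SA3's stated product.

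A reader might also infer that the evening questionnaires break the SA1 blind, since they include "a 20-item questionnaire that assesses the impact of atrial fibrillation on quality of life" and drug use. The documents do not show this. No section says that the staff who collect forms score the PSG or read the echoes, and the form is not restricted to cases.

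**Conclusion.** The concern holds for SA3. Masking to visit and CPAP is not provided for AF paroxysm scoring and is not specified for echo, in a design with no control group to absorb a reading shift. The size of any bias is unknown. On the plan's own variance assumptions, and with assumed shifts of 5% or 10% in AF counts applied consistently, the chance of a spurious p<0.05 rises from 5% to about 13% or 38%. These figures show sensitivity and are not an estimate of what will happen.

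For SA1 the risk is smaller: the ECG channel can reveal status only for cases in AF that night, and the documents give no frequency. The stronger inference that the primary exposure is generally open to biased scoring is not supported, because scorers are certified, follow standard procedures and are blinded to identity.

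The change should be made. It alters neither sample size nor analysis.

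**What to change.** 1. **Echo.** State that the Section 8 blind covers visit and CPAP as well as PAF status. For SA3 patients, have the same reader measure both archived studies, stripped of date and visit, in random order. Mixing them with other participants' coded studies would keep a pair from being recognisable.
2. **AF paroxysms.** Take the final SA3 counts from stored recordings under a code that hides visit and CPAP. Real-time safety monitoring under Section 11 stays as it is.
3. **PSG.** Hide the ECG trace while respiratory events are scored, after checking that the scoring manual agrees with the Section 8 definitions in not using it. The signal still goes to the electrophysiology core for HRV.

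Cost: research echo measurements for SA3 patients wait about three months. If the technicians who monitor in real time also produce the counts, a coded rescoring pass may be needed, at most 75 × 2 = 150 recordings at the planned SA3 size. The rest is protocol and manual wording, using existing readers and archived files.
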